15.12 Nursing guidelines

Educate patient regarding this protocol and address questions.

1. Instruct patients to report any rash or burning with application
2. Instruct patients to avoid eye contact after applying lotion
3. Agent should be stored at room temperature

16.0 Statistical Considerations and Methodology

16.1 Primary

This is a randomized, two arm, placebo-controlled, double-blind, pilot study of whether CBD can improve CIPN more than a placebo. The purpose of this pilot study is to estimate the treatment effects of CBD compared to the placebo arm. These preliminary efficacy estimates will aid in the design of a large-scale randomized phase III clinical trial.

The primary endpoint is the change in CIPN from baseline to week 2. CIPN will be measured by the sensory subscale of the EORTC QLQ-CIPN20 which is composed of 9 individual items. Secondary endpoints include other measures of neuropathy as measured by the EORTC QLQ CIPN20 motor subscale, the EORTC QLQ CIPN20 autonomic scale, and the CTCAE neuropathy scale. Adverse event profiles will also be assessed using symptom questionnaires and the CTCAE 5.0.

As this is a pilot study, descriptive statistics and statistical plots will be utilized to summarize and estimate the primary and secondary endpoints. Statistical hypothesis testing will be used in an exploratory manner and will be interpreted accordingly.

For the primary analysis, changes in sensory neuropathy from baseline to week 2 will be compared between arms using two-sample, two-sided t-tests. The CBD arm will be compared to the placebo arm. We will construct 95% confidence intervals for the mean difference in sensory neuropathy score between arms. Repeated measures mixed models will be applied to the sensory scores over all time points to determine longitudinal effects and to adjust for confounding factors. Graphical results will include profile plots over time, stream plots of individual changes over time, and forest plots of the 95% confidence intervals by arm.

For logistical and financial reasons, the sample size for this pilot study is set at 40 patients (20 per treatment group). While this is only a descriptive study and is not powered to detect significant differences between arms, the following table provides power analyses for various effect sizes based on a two-sided, two-sample t test at $\alpha = 0.05$ for a fixed sample size of 20 patients per arm.

Effect size, $\Delta = \mu_1 - \mu_2 / \sigma$	0.5	0.6	0.7	0.8	0.9	1.0
Power	0.34	0.46	0.58	0.69	0.79	0.87

For example, we will have 79% power to detect an effect size of 0.9 in EORTC QLQ-CIPN20 with a sample size of 40 patients (20 per arm). This effect size is the mean difference divided by the common standard deviation within each arm.

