2.0 Goals

This is a pilot randomized double blinded placebo controlled cross-over trial. This pilot study will randomize 40 patients with chemotherapy-induced peripheral neuropathy to receive, for 14 days, either 1) a CBD cream or 2) a placebo. Patients initially receiving the placebo will cross over to receive the CBD cream, while those receiving the CBD creams will cross over to receive the placebo, for 14 days. Patients will apply cream to the affected area (hands and/or feet) twice daily (morning and evening). This cross-over will allow all patients to eventually receive the CBD cream and will allow us to determine whether any benefit derived from a CBD preparation will diminish or persist after the CBD preparation is stopped (that is in the patients who initially received the CBD product and then were changed to receive a placebo, while still being blinded to what they received).

No washout period is planned with the cross-over because a) no washout is needed in patients going from placebo to CBD cream, and b) we want to determine what happens after patients stop cannabis cream, i.e., do the effects persist after the patient starts the placebo portion, as was prominently seen in a prior trial of ours evaluating capsaicin cream [30].

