14.0 Body Fluid Biospecimens – None.**15.0 Drug Information**

Placebo and creams will be provided by Nightingale Remedies. This product has been tested by an independent lab for content and has 0% THC (testing attached). The study cream contains CBD isolate; both creams are odorless. 4-5 pumps of product will cover hands/feet and contains approximately 4 mg of CBD isolate. Patients with CIPN only on hands or feet would then get approximately 8 mg of topical CBD per day. Patients with CIPN on both locations would get approximately 16 mg of topical CBD per day. See appendix VII for product ingredients. See investigator brochure for detailed information about drug product and safety issues.

[figure not shown]
Shipping, handling, and storage

Creams should be stored at room temperature (59°-77°F). Product will be shipped from Nightingale Remedies to participating sites. They will not be blinded to their local pharmacist who must keep all of the other clinical partners blinded to the study product and placebo.

IND number: 157457

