Appendix I: EORTC QLQ-CIPN20 Instrument

ENGLISH

EORTC QLQ – CIPN20

Patients sometimes report that they have the following symptoms or problems. Please indicate the extent to which you have experienced these symptoms or problems during the past week. Please answer by circling the number that best applies to you.

During the past week :	Not at All	A Little	Quite a Bit	Very Much
31 Did you have tingling fingers or hands?	1	2	3	4
32 Did you have tingling toes or feet?	1	2	3	4
33 Did you have numbness in your fingers or hands?	1	2	3	4
34 Did you have numbness in your toes or feet?	1	2	3	4
35 Did you have shooting or burning pain in your fingers or hands?	1	2	3	4
36 Did you have shooting or burning pain in your toes or feet?	1	2	3	4
37 Did you have cramps in your hands?	1	2	3	4
38 Did you have cramps in your feet?	1	2	3	4
39 Did you have problems standing or walking because of difficulty feeling the ground under your feet?	1	2	3	4
40 Did you have difficulty distinguishing between hot and cold water?	1	2	3	4
41 Did you have a problem holding a pen, which made writing difficult?	1	2	3	4
42 Did you have difficulty manipulating small objects with your fingers (for example, fastening small buttons)?	1	2	3	4
43 Did you have difficulty opening a jar or bottle because of weakness in your hands?	1	2	3	4
44 Did you have difficulty walking because your feet dropped downwards?	1	2	3	4

Please go on to the next page

During the past week :

	Not at All	A Little	Quite a Bit	Very Much
45 Did you have difficulty climbing stairs or getting up out of a chair because of weakness in your legs?	1	2	3	4
46 Were you dizzy when standing up from a sitting or lying position?	1	2	3	4
47 Did you have blurred vision?	1	2	3	4
48 Did you have difficulty hearing?	1	2	3	4

Please answer the following question only if you drive a car

49 Did you have difficulty using the pedals?	1	2	3	4
--	---	---	---	---

Please answer the following question only if you are a man

50 Did you have difficulty getting or maintaining an erection?	1	2	3	4
--	---	---	---	---

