Appendix IV: Peripheral Neuropathy Question

1. How much of a problem has tingling or pain in your fingers and/or toes been in the past week?

0 **1** **2**

No tingling or pain
in fingers and/or
toes

3

4

5

6

7

8

9

10

[figure not shown]
Tingling or pain in
fingers and/or toes
as bad as you can
imagine

DRAFT

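### The cream goes only on the affected hands and/or feet, but the primary score pools hand and foot items for every patient, so the same local benefit counts about half in a one-site patient and no analysis uses treated site

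*Combined protocol and SAP*

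**What the plan says.** Application is site-specific. Sections 2.0 and 7.1 have patients treat the affected area, which may be hands, feet or both. Section 15.0 plans for both kinds of patient: "Patients with CIPN only on hands or feet would then get approximately 8 mg of topical CBD per day", and "Patients with CIPN on both locations would get approximately 16 mg of topical CBD per day". Eligibility does not require both sites. Criterion 3.14 asks for at least 4 out of 10 on the single Appendix IV question, "How much of a problem has tingling or pain in your fingers and/or toes been in the past week".

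The primary measure is not site-specific. Section 16.1 states: "CIPN will be measured by the sensory subscale of the EORTC QLQ-CIPN20 which is composed of 9 individual items". The change in this score from baseline to week 2 is compared between arms by a two-sample t-test. Appendix I asks about the sites separately, for example "Did you have tingling fingers or hands" and "Did you have tingling toes or feet". It does the same for numbness and for shooting or burning pain, and it adds a further foot item, "Did you have problems standing or walking because of difficulty feeling the ground under your feet".

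Treated site does not appear in the section 4.1 schedule, the stratification (gender only, sections 5.0 and 6.4d), the analyses in 16.1 and 16.2, or the subset analyses in 16.42. The mixed model in 16.1 adjusts for confounders that are not named. The case report forms are not part of the documents.

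**The concern.** In a feet-only patient the hand items should sit at or near the lowest category, and the hands receive no cream, so those items have little room to improve. They still enter the score. Two patients with the same relief where the cream was applied can therefore show quite different changes in the primary score, depending only on how many sites were affected.

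This matters because section 16.1 gives the trial's purpose as estimating the treatment effect to help design a phase III trial. A mean difference in raw score points mixes the local effect of the cream with the share of one-site patients. That share is neither stated nor planned to be reported, so a phase III team could not separate the two.

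**Working it through.** **The plan's own figure.** For a two-sided t-test at 0.05 with 20 per arm, exact noncentral-t power (38 df, noncentrality d × √10) at effect sizes 0.5 to 1.0 is 0.338, 0.456, 0.578, 0.693, 0.792, 0.869. The table in 16.1 gives 0.34, 0.46, 0.58, 0.69, 0.79, 0.87. It reproduces.

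**Assumptions.** The documents give neither the nine items nor the scoring rule. I assume:
- score = (sum of nine items − 9) / 27 × 100, so one category on one item is 100/27 = 3.7 points;
- hand items 31, 33, 35 and foot items 32, 34, 36, 39 are among the nine;
- item 40 (hot and cold water) is also among them and names no site.

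**Score change for a one-category gain on every treated-site item.**

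| Treated | Item 40 left out | Item 40 improves in all |
|---|---|---|
| Both | 7/27 = 25.9 | 8/27 = 29.6 |
| Feet only | 4/27 = 14.8 | 5/27 = 18.5 |
| Hands only | 3/27 = 11.1 | 4/27 = 14.8 |
| Ratio to both, feet only | 4/7 = 0.57 | 5/8 = 0.63 |
| Ratio to both, hands only | 3/7 = 0.43 | 4/8 = 0.50 |

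If only the three matched pairs (items 31 to 36) respond, the changes are 6/27 = 22.2 and 3/27 = 11.1, a ratio of 0.50.

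**Spread due to site alone in the CBD arm.** For a share f of feet-only patients, the rest two-site, with item 40 left out, the gap is 25.9 − 14.8 = 11.1 points and the SD is 11.1 × √(f(1 − f)):
- f = 0: 0
- f = 0.10: 11.1 × 0.30 = 3.3
- f = 0.50 (the maximum): 11.1 × 0.50 = 5.6

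The gap is proportional to the assumed gain, so a smaller effect gives a smaller SD. For hands-only patients the gap is 25.9 − 11.1 = 14.8 and the same formula applies.

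**Power.** Suppose 0.9 SD is the effect in an all-two-site population and r is the one-site to two-site ratio. The diluted effect is d = 0.9 × (1 − f(1 − r)). At f = 0.50:
- SD unchanged: d = 0.643 and power 0.51 at r = 0.43; d = 0.707 and power 0.59 at r = 0.57.
- One-site SD shrinks in the same ratio, so d is divided by √((1 − f) + f r²): d = 0.836 and power 0.73; d = 0.868 and power 0.76.

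**Chance imbalance.** If half the patients are one-site and site is not stratified, a difference of 4 or more one-site patients between two arms of 20 has probability about 0.27 (two independent binomials).

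**Treated-site score.** The mean of the treated-site items changes by 7/7, 4/4 or 3/3 = 1 category for both, feet only or hands only. The ratio is 1 whatever the site mix.

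**The case against.** The best defence is that overall sensory burden on a named subscale is a legitimate target. A phase III trial with the same eligibility could enrol a similar mix, in which case the pooled estimate would carry over. The pilot is also declared descriptive and not powered. This stands, and it is why the subscale should remain primary.

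The added spread is also modest. With half feet-only, the mean change is (25.9 + 14.8)/2 = 20.4 and the site SD is 5.6. At an effect of 0.9σ, that SD is 0.9 × 5.6/20.4 = 0.25σ, which raises the CBD-arm SD by √(1 + 0.25²), about 3%. This stands too.

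A reader might go further in four ways that the documents do not support:
- **The benefit always counts half or less.** On a consistent item count, feet-only patients come out at 0.57 or 0.63 of a two-site patient.
- **The comparison is biased.** Randomisation balances site on average. A chance imbalance is possible, but that is not bias.
- **Power is lost.** Items at floor may add little variance, and power then stays near the stated 0.79.
- **An imbalance in site could not be seen.** The baseline CIPN20 asks about hands and feet separately, so affected site can largely be inferred. Unseen forms may also record it. Inference is still not a record of where cream was applied, and no such summary is planned.

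**Conclusion.** The mismatch holds: treatment is site-specific, the primary score is not, and no planned analysis uses treated site. Under the assumed items and equal-weight scoring, a given local benefit counts about half in a one-site patient (0.43 to 0.57, or 0.50 to 0.63 with item 40).

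How much this matters depends on the share of one-site patients, which the documents do not give. With no such patients there is no effect. Under a full one-category gain, the site-related SD is about 3.3 points at 10% feet-only and 5.6 at 50%. The consequence is a raw effect estimate for phase III that is attenuated and varies with site mix. The power table is correct, and nothing here invalidates the primary comparison. The point is a worthwhile low-cost improvement, not a flaw in the main analysis.

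**What to change.** - In section 4.1, record the treated site(s) as hands, feet or both at Day 1, before the first application. Tabulate them by arm.
- In section 16.1, list the nine sensory items and the scoring rule.
- In section 16.2, add one supportive endpoint: change from baseline to week 2 in the mean of CIPN20 items 31, 33, 35 (hands treated) and/or 32, 34, 36, 39 (feet treated). Use only the site(s) recorded at Day 1 and analyse it like the primary.
- Keep the full sensory subscale as primary.

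The cost is one form field and one extra descriptive analysis of items already collected, with no added patient burden. The downside is that the treated-site score is not the published subscale, so it can only support the primary result.

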3.0 Registration Patient Eligibility

3.1 Registration - Inclusion Criteria

- 3.11 Age \geq 18 years
- 3.12 English speaking
- 3.13 Cancer diagnosis of any tumor type with chemotherapy-induced neuropathy
- 3.14 At least 4 out of 10 severity of neuropathy pain and/or tingling per appendix IV
- 3.15 Stable for at least 7 days prior to registration on medications for neuropathy, if any are being used
- 3.16 ECOG Performance Status (PS) 0, 1 or 2 (Appendix VIII).
- 3.17 **Negative pregnancy test done \leq 7 days prior to registration, for persons of childbearing potential only.**

NOTE: If a urine test is positive or cannot be confirmed as negative, a serum pregnancy test will be required.

- 3.18 Able to provide written informed consent
- 3.19a Ability to complete questionnaire(s) by themselves or with assistance.
- 3.19b No evidence of residual cancer
- 3.19c Required Initial Laboratory Values: Following completion of chemotherapy, patients must have had a CBC and serum chemistries, including the following:
 - Platelet count $>$ 100,000/mm³
 - Absolute neutrophil count (ANC) \geq 1,000/mm³
 - Hemoglobin $>$ 11 g/dL
 - Serum transaminase [ALT or AST] \leq 1.2 x upper limit of normal (ULN)
 - Alkaline phosphatase \leq 1.2 x ULN
 - Serum creatinine \leq 1.2 x ULN

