4.0 Test Schedule

4.1 Test schedule for Chemotherapy-Induced Peripheral Neuropathy

Study Visit	1	2	3	4	5	6	7
Study Time Point	Screening /Baseline (Day -30 to Day 1)	Day 1	End of Week 1	End of Week 2 ^c (+3 Days)	End of Week 3	End of Week 4	End of study
CLINICAL ASSESSMENTS							
Informed consent	X						
Inclusion/exclusion criteria	X ^g						
Demographics/ Medical history	X						
Pregnancy testing ^a	X						
Randomization	X						
Dispense Study Product/Placebo		X		X			
Collect questionnaires							X
Adverse event assessment ^b			X	X	X	X	
STUDY TESTING							
EORTC QLQ-CIPN 20 instrument (Appendix I)	X		X	X	X	X	
Global impression of change (Appendix II)			X	X	X	X	
Chemotherapy Induced Peripheral Neuropathy Assessment Tool (Appendix III)	X		X	X	X	X	
Symptom experience diary (Appendix Va & Vb)	X ^d		X ^e	X ^e	X ^e	X ^e	
NCI-CTCAE neuropathy scale ^f (Appendix VI)	X		X	X	X	X	
Cycle = 14 days							
^a For individuals of childbearing potential. Must be done \leq 7 days prior to registration.							
^b Research nurse or clinician to call patient. Including inquiry about skin toxicity and to assess for suicidal thoughts (Appendix IX). Ask the patient if they have missed any doses of the study							

medication and provide education if necessary. Note any other pertinent information that the patient provides.

^c After subject completes week 2 they will turn in completed questionnaire diary and start the next supply of cream within 1-3 days after completing the first 2 weeks, ideally.

^d Appendix Va: System Experience Diary used for baseline assessment. Must be completed prior to application of study medication.

^e Appendix Vb: System Experience Diary used for weekly assessments. Must be completed at the end of each week.

^f To be completed during research nurse or clinician call to patient per Appendix VI.

^g Required Initial Laboratory Values per inclusion criteria 3.19c can be done any time after the patient has completed their chemotherapy and prior to study registration.

5.0 Stratification Factors:

- Gender (Male, Female, or Other)

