6.4d Randomization Procedures: The factor defined in Section 5.0 (gender) will be used as the only stratification factor

6.4e Procedures for Double-Blinding the Treatment Assignment

6.4e1 After the treatment assignment has been ascertained by the registration/randomization application, the registration specialist will notify the designated unblinded data manager/nurse/pharmacist at the patient's institution. The name of this contact person is to be entered in the designated space on the eligibility checklist at the time of registration. Make sure this contact person will be available at the time of registration so he or she can be contacted by the registration specialist if necessary. This contact person may not be involved in assessing adverse events or any other outcome measure and should not be the same person listed on page one of the Eligibility Checklist Form as the person completing the form. The last page of the Eligibility Checklist Form should provide the sources of communication, either fax or e-mail, and the appropriate contact information. The registration specialist will then communicate the treatment assignment to the designated contact at the patient's institution.

6.4e2 The treatment assignment will be to *active or placebo*. The unblinded pharmacist should only give one supply of study cream at a time according to the treatment assignment from the registration specialist. Each participating institution will be responsible for monitoring drug supplies. The bottles will be labeled by the unblinded pharmacist as "*CBD or placebo cream*" so that the contents are not discernible to the person administering the treatment. At the time of cross-over, the patient will be given the alternative medication (CBD or placebo), again in a blinded manner.

6.4e3 The unblinded pharmacist will maintain records that indicate the identity of the patient and their corresponding treatment assignment.

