16.2 Analysis Plan for Secondary Outcome and Translational Endpoint

Analyses for secondary endpoints will also be descriptive in nature. Due to the exploratory nature of this research, we will not adjust for multiple comparisons for the secondary analyses. Analyses of the motor and autonomic subscales will be identical to the analyses of the primary endpoint. Analyses of CTCAE grades and the symptom questionnaire individual items will compare the incidence and maximum (worst) values between arms. Fisher's exact tests will be used to compare incidence rates and Wilcoxon rank-sum tests will be used to compare maximum values between arms.

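### The primary t-test on change fixes the baseline slope at 1 and leaves out gender, the only stratification factor; a baseline- and gender-adjusted ANCOVA would give this 40-patient estimation study a better primary estimate at very little cost.

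*Combined protocol and SAP*

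**What the plan says.** Section 16.1 defines the endpoint and the test: "The primary endpoint is the change in CIPN from baseline to week 2", and "changes in sensory neuropathy from baseline to week 2 will be compared between arms using two-sample, two-sided t-tests". It adds a 95% confidence interval for the mean difference between arms. No covariate is mentioned for this comparison.

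The same section gives the aim: "The purpose of this pilot study is to estimate the treatment effects of CBD compared to the placebo arm". The estimates are meant to help design a phase III trial, and hypothesis testing is described as exploratory.

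Section 16.1 also plans a second analysis: "Repeated measures mixed models will be applied to the sensory scores over all time points to determine longitudinal effects and to adjust for confounding factors". It does not name the confounding factors or define a week-2 contrast from the model.

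Section 5.0 lists gender, with three levels, as the stratification factor. Section 6.4d confirms it: "The factor defined in Section 5.0 (gender) will be used as the only stratification factor". No analysis in section 16 names gender as a covariate.

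Section 16.2 carries the approach over to secondary endpoints: "Analyses of the motor and autonomic subscales will be identical to the analyses of the primary endpoint".

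**The concern.** A t-test on change is a regression of the week-2 score on arm with the baseline coefficient forced to 1. If the true coefficient is lower, the change score over-corrects for any baseline difference between the arms. Averaged over randomisations this cancels, so the test is unbiased. In the one trial that is run, the estimate is shifted by an amount that depends on the observed imbalance.

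The documents give reasons to expect a slope below 1, though no figure for it. Appendix VII describes CIPN symptoms as commonly fluctuating. The test schedule in section 4.1 allows baseline to be collected over a window of about 30 days. Section 3.1 enrols on a symptom threshold ("At least 4 out of 10 severity of neuropathy pain and/or tingling per appendix IV"), which invites regression to the mean.

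At stake are the point estimate and the interval, which are the main products of this pilot. Leaving gender out also means that the analysis does not follow the randomisation design.

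**Working it through.** **Inputs from the documents.** 20 per arm, two-sided alpha 0.05, two-sample t-test on change (16.1); gender as the only stratification factor, with three levels (5.0, 6.4d). **Not in the documents, so assumed:** the correlation rho between baseline and week-2 sensory scores, and k, the ratio of baseline SD to week-2 SD. All figures assume 40 evaluable patients.

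**Step 1: the plan's own figures.** A noncentral t calculation with 38 df and standard error sqrt(2/20) = 0.316 gives power of 0.338, 0.456, 0.578, 0.693, 0.792 and 0.869 at effect sizes 0.5 to 1.0. All six entries of the table in 16.1 reproduce.

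**Step 2: interval width with equal variances (k = 1).** In units of the change-score SD, the expected half-width with p covariates is

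t(0.975, 38 − p) × s × sqrt(0.1 × (1 + p/(37 − p))).

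For the t-test, p = 0 and s = 1, so the half-width is 2.024 × 0.316 = 0.640. For ANCOVA, s = sqrt((1 − rho²)/(2(1 − rho))) = sqrt((1 + rho)/2). The factor 1 + p/(37 − p) is the small-sample cost when covariates differ between arms at random. Gender is taken as non-prognostic, so it can only cost precision here.

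| rho | baseline only (p = 1) | narrower by | baseline + 2-level gender (p = 2) | narrower by | baseline + 3-level gender (p = 3) | narrower by |
|---|---|---|---|---|---|---|
| 0.3 | 0.524 | 18% | 0.532 | 17% | 0.540 | 16% |
| 0.5 | 0.563 | 12% | 0.571 | 11% | 0.580 | 9% |
| 0.7 | 0.599 | 6% | 0.608 | 5% | 0.617 | 4% |
| 0.8 | 0.616 | 4% | 0.626 | 2% | 0.635 | 1% |

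The gain vanishes at rho = 0.94, 0.88 and 0.83 for p = 1, 2 and 3.

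Stratification should balance gender within arm, and then the gender term costs almost nothing. In simulation (8,000 runs, gender balanced and non-prognostic), baseline plus two-level gender was 12.2%, 6.4% and 3.7% narrower at rho 0.5, 0.7 and 0.8. With a two-patient third level the figures were 12.0%, 6.3% and 3.5%.

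**Step 3: unequal variances.** If the entry threshold compresses baseline spread, the change SD is sqrt(k² + 1 − 2k·rho) and the ANCOVA SD is sqrt(1 − rho²), in week-2 SDs. At k = 0.8 and rho = 0.5 these are 0.917 and 0.866. Change in interval width at k = 0.8 (positive means narrower):

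| rho | slope rho/k | baseline only | + 2-level gender, unbalanced |
|---|---|---|---|
| 0.5 | 0.625 | +4.1% | +2.7% |
| 0.6 | 0.75 | +1.6% | +0.1% |
| 0.7 | 0.875 | −0.5% | −2.0% |
| 0.8 | 1.0 | −1.5% | −3.0% |

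In the opposite case, k = 1.25, baseline adjustment narrows the interval by 19% to 26% over rho 0.4 to 0.8.

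**Step 4: the worst case.** If the slope is exactly 1, the two SDs are equal and only the covariate cost remains. For p = 1 it is (2.0262/2.0244) × sqrt(1.0278) = 1.015, or 1.5% wider. For p = 2 it is 3.0%, and for p = 3 it is 4.6%.

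**Step 5: conditional shift (k = 1).** A one-standard-error baseline imbalance is 0.316 SD. It shifts the change-score difference by (1 − rho) × 0.316:

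| rho | shift (score SD) | t-test half-width (score SD) | shift / half-width |
|---|---|---|---|
| 0.5 | 0.158 | 0.640 | 25% |
| 0.7 | 0.095 | 0.496 | 19% |
| 0.8 | 0.063 | 0.405 | 16% |

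The shift is zero when the slope rho/k equals 1.

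**The case against.** The best defence is that nothing here is wrong. The endpoint, test and power table agree with one another, the t-test is valid, and section 16.1 calls the study descriptive and not powered to detect differences. No go/no-go rule depends on the interval. All of that stands, and it makes this a recommended improvement and not an error.

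Four further points have weight:

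- **Width and conditional shift are one quantity.** With equal variances, 2(1 − rho) − (1 − rho²) = (1 − rho)², so the extra variance of the change score is the squared shift in step 5 (both scaled by 2/20). The t-test interval already covers it. Steps 2 and 5 must not be added together.
- **The gain is not assured.** It depends on rho and k, and at k = 0.8 with a high rho it turns into a small loss. The entry threshold also applies to the single Appendix IV item, not to the CIPN20 sensory score, so compression of the baseline SD is itself an assumption.
- **The gender term has no demonstrated precision gain.** An assumed 0.5 SD gender effect at rho 0.6 lowered the simulated half-width from about 0.60 to 0.58 change-score SDs and left the unadjusted t-test slightly conservative (type I error 0.042), but the documents support no such effect. The accrual targets in 16.43 foresee only females and males, so a third level may be empty.
- **The mixed model might handle baseline.** If it includes baseline as an outcome or covariate, it could estimate the slope. As written, its covariates are unnamed, it runs across the post-crossover weeks, and it is not the primary analysis. It reduces the concern without removing it.

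None of these gives a reason to prefer a fixed slope when the alternative costs so little.

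**Conclusion.** The concern holds as an efficiency and design-consistency point. With equal variances, baseline adjustment narrows the primary interval by 4% to 18% for rho between 0.8 and 0.3. With two-level balanced gender added, it is about 4% to 12% for rho between 0.8 and 0.5. The expected loss if the slope is 1 is 1.5% to 4.6%, depending on how many covariate terms are used and assuming no benefit from stratified balance. Adjustment also removes the linear part of the shift caused by whatever baseline imbalance occurs.

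Most of the benefit comes from baseline; gender belongs in the model because it was used to stratify. Confidence in the size of the gain is medium, because rho and k are assumptions throughout. The t-test and the power table need no correction.

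**What to change.** Change section 16.1 so that the primary estimate is an ANCOVA of the week-2 sensory score (or, equivalently for the treatment effect, the change) on arm, baseline sensory score and gender, reported as an adjusted mean difference with its 95% confidence interval. State before unblinding how a sparse or empty third gender level will be pooled. Keep the two-sample t-test on change as a supporting analysis; the power table can stay with it.

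Name the covariates of the repeated-measures model. Apply the same ANCOVA to the motor and autonomic subscales, which 16.2 ties to the primary analysis.

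The cost is SAP wording only, since baseline score and gender are already collected. The model uses two further degrees of freedom, or three if the third gender level is kept separate; the t critical value rises from 2.024 to 2.028 or 2.030.
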